7.2 Power Considerations

Since this is a feasibility study our main outcome is to assess accrual, retention, attrition, measure sensitivity, and effect size for the multi-component intervention. A sample of 15 participants per arm will allow us to design estimates that we can use for the development of a larger study.

8.0 Protection of Human Subjects

8.1 Sources of Material

The sources of material include data obtained from questionnaires. Data collected from participants will include the standardized questionnaires as described in the research plan. Additionally, participants will be asked to provide demographic and contact information. All data are collected for research purposes only, as part of the proposed study. All data will be kept completely confidential and referenced only in terms of a coded research assigned number. Data will be entered into a statistical database (SAS, Stata or SPSS) that is password protected and accessed on a hard drive protected by a fire wall. A unique study number will be given to each participant. This will ensure the confidentiality of the participants.

8.2 Potential Risks

Study visits and forms: Participants may be inconvenienced by the completion of forms, phone calls, and virtual study visits. We will make every attempt to work around the schedules of participants and to minimize burden on patients with respect to forms and follow up phone calls.

This study presents minimal potential risks to participants. Participants may choose to not participate in any part of this voluntary study. Potential risks include agitation and anxiety which we will try to minimize by ensuring participants understand how to use the intervention including additional relaxation exercises included in the study materials. Participant may have discomfort during completion of study questionnaires, frustration with the intervention due to lack of perceived benefit, which we will try to minimize through participant education on the purpose of the study. Further, with the vaginal moisturizer, participants may develop a vulvar rash or irritation; they may experience burning or itching; or they may experience a vaginal infection.

Risks associated with this trial will be kept to a minimum and all participants will be monitored carefully. Patients will be reminded that they can discontinue study participation at any time they choose or if their primary doctor feels it is in their best

interest to stop. Participation in this research study is strictly voluntary. The participant may opt to withdraw consent at any time for any reason. The investigator will notify the participant of any new information related to risk, toxicity, or efficacy that could influence the decision by the participant or investigator to continue study therapy.

Confidentiality: Any information about the participant obtained from this research will be kept confidential. Participants will not be identified by name in any publication or presentation resulting from the study. A code will be assigned to each participant that will allow for tracing the identity of each study participant. The IRB and Data Safety and Monitoring Committee will assess confidentiality and safety throughout the study period. Participant data will be stored using UTK encrypted servers and/or in locked files. Only IRB approved research staff will have access to participant files. All data will be de-identified and coded with study numbers.

Research team members are trained in the intervention and work directly under the supervision of [name] and [name]. Measures will be taken to ensure each participant understands their right to withdraw from the study at any time for any reason. Participants will be gently coached using behavioral change theory to implement their assigned study treatment as designed but at no time will participant be made to feel guilty about or pressured to implement the study procedures in any way. If the research therapists assess at any time that study participation is causing an undue burden on a participant, they will address this issue and again assure the participant of their right to withdraw.

Participants will be notified of any potential breach of personal information, should it occur.

All study records will be retained per institution policy.

8.3 Compensation for Participants

Participants will be compensated individually for their participation in this research study and may receive up to a total of \$80 compensation. Compensation will be prorated at \$20 for each two-week period which includes completion of data, the phone call and AE assessment. After completion of the study, participants will be sent their compensation in the form of gift cards.

8.4 Protection of Human Subjects Training

All research personnel will complete human participant protection training through CITI.

8.5 Potential benefits of the Proposed Research to Human Subjects and Others

Potential benefits of study participation may include improvement in sexual function, but improvement is in no way guaranteed.

8.6 Importance of Knowledge to Be Gained

Data from this study will provide critical information about how to design a well powered efficacy study that assesses the impact on sexual function and satisfaction from addressing more than one element of decreased sexual function. These data will add to

the science that will likely increase the development of other intervention studies trying to address this critical issue.

9.0 Data and Safety Monitoring

The study team will meet every six months or more frequently depending on the activity of the protocol. The discussion will include matters related to the safety of study participants (SAE/UaP reporting), validity and integrity of the data, enrollment rate relative to expectations, characteristics of participants, retention of participants, adherence to the protocol (potential or real protocol deviations), and data completeness. These regular meetings will be documented and result in a Data and Safety Monitoring Report form that will be completed and signed by the Principal Investigator or by one of the co-investigators. These reports will be filed with the IRB during the scheduled continuing review.

10.0 Adverse Event Reporting

Oversight of the progress and safety of the trial will be provided by the PI and Co-I. This study presents minimal risk to subjects. Adverse events (AEs) are not anticipated; however, study staff will assess AEs during follow up phone calls. Any occurring AEs will be documented using the CTCAE version 5 and reported to the IRB per institutional guidelines.

References

1. American Cancer Society. *Cancer Treatment & Survivorship Facts & Figures 2019-2021*. Atlanta: American Cancer Society;2019.
2. American Cancer Society. *Cancer Facts & Figures 2022*. Atlanta: American Cancer Society;2022.
3. National Institutes of Health State-of-the-Science Conference statement: management of menopause-related symptoms. *Ann Intern Med*. 2005;142(12 Pt 1):1003-1013.
7. Young-McCaughan S. Sexual functioning in women with breast cancer after treatment with adjuvant therapy. *Cancer Nurs*. 1996;19(4):308-319.

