3.0 Preliminary Data

In this section, we will review the existing data for treatment of vulvovaginal atrophy (VVA), libido, and body image. These three components are the focus of this proof-of-concept study.

Vulvovaginal symptoms are consistently identified as predictors of sexual health concerns in female cancer patients and survivors.^{8,19-21} The vagina is highly regulated by estrogen and cancer treatments causing estrogen deprivation result in vulvovaginal dryness and discomfort, bleeding after intercourse, and increased susceptibility to infections, all of which can negatively impact enjoyment and interest in sexual intimacy.²²

Standard/current treatment

The initial treatment for VVA symptoms focuses on non-hormonal treatments to improve tissue quality. Vaginal moisturizers, involving bases such as polycarbophil, hyaluronic acid (HLA), gums or gelatins, may be used on a regular basis for hydrating vaginal tissue. Moisturizers have been shown to stabilize vaginal pH in limited studies and demonstrated efficacy against VVA symptoms.²³ Ospemifene, a Food and Drug Administration-approved selective estrogen receptor modifier (SERM) for dyspareunia, is associated with potential adverse effects including hot flashes and venous thromboembolic events,²⁴ and has not been proven safe for women with breast malignancies. Water- or silicone-based lubricants are also suggested to decrease friction and enhance comfort with sexual touch and activity including vaginal insertion.

The gold standard in the general population if women do not respond to non-hormonal treatment is vaginal estrogen. Initially, the lowest dose possible (eg: 7.5 micrograms [mcg] suppository) is used to provide symptom relief while minimizing systemic effects.^{24,25} Although very low dose vaginal estrogen may not result in systemic concentrations outside of the menopausal range, research has shown significant changes in lipids and bone biomarkers, suggesting systemic effects related to estrogen may indeed occur.^{26,27}

Vaginal estrogens given to women on aromatase inhibitors (AIs) may be absorbed through the vaginal mucosa, resulting in significantly increased circulating levels and systemic effects.²⁸ Therefore for many women with a history of breast cancer, use of low dose vaginal estrogen is a last resort, reserved for when nothing else has been helpful.

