4.2 Subject Recruitment

Recruitment and screening: Potential participants from the community will be identified in three ways: (1) physician referrals; (2) ResearchMatch.org; and (3) study advertisements including social media campaign, radio ads, flyers/brochures and a study website. Flyers may be posted in the greater Knoxville area. Locations such as churches, gyms, and cancer support groups. Brochures and flyers may be provided to physicians, providers, and organizations to distribute. IRB-approved recruitment materials may be posted on social media or in University of Tennessee/non-University of Tennessee newspapers, newsletters or websites, or read over WUOT. Participant eligibility will be determined using the Screening Eligibility Check List created from the criteria listed in 4.3.

Baseline visit: If a woman is screened eligible using the screening eligibility checklist, she will be mailed or emailed the consent form and scheduled for a virtual baseline visit. Baseline visits will be conducted using a HIPAA compliant platform (video or phone). The purpose of the baseline visit is to ensure that participants understand the study requirements, have their questions answered, be consented, complete baseline questionnaires, and are randomized. After confirming eligibility and reviewing the consent, eligible women will sign the consent using an IRB approved e-consent platform. After consent is attained, participants will be given a study number. Then baseline questionnaires will be completed, women will be randomized to vulvovaginal treatment with hypnosis starting in two weeks or vulvovaginal treatment control. Randomization will be done at the time of consent using a random number generator with “1” being the intervention group and “2” being the control group. They will then be educated about treatment with a vaginal moisturizer (see intervention details below). This treatment will begin within two weeks of completing the baseline visit (to allow for shipping of the moisturizer) and will be verified with the study coordinator. The start of vulvovaginal treatment will be confirmed by the study coordinator either through an email or phone communication with the participant. After confirmation of the start of vaginal moisturizer treatment, behavior education visit (Intervention) or follow up phone call (Control) will be planned for two weeks (+/- 3 days) for both groups.

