Behavioral education visit: After treatment for vulvovaginal dryness has been underway for two weeks for the intervention group and VVA control group, a second remote visit will be conducted to assess how the vaginal treatment is progressing and to answer any questions about use of the moisturizer and assess for any adverse events. Also, during this second remote visit, the intervention group will be educated about the hypnotic induction intervention (see intervention information below). The rationale for splitting this education into a second visit is two-fold. First, doing it during the baseline visit would make that visit too long and too complex. It is likely participants would be overwhelmed with all of the information. Secondly, since the treatment for vulvovaginal

atrophy will take eight weeks for large effects to be seen, it is important the treatment get started and women get into that routine before adding a behavioral component. It is a standard approach in complex behavioral change to take a stepwise approach.

Phone follow up calls: Participants in both groups will have follow-up calls every two weeks (+/- 3 days) during the intervention except the week of the behavioral education visit to assess for adverse events, problem solve any lack of adherence, ensure completion of data collection and enhance study engagement.

A Screening and Enrollment Log will be maintained to document eligibility/ineligibility, screen dates, consent dates, and referral source of each individual screened.

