4.3.1. Inclusion Criteria

1. Age \geq 18 female
2. History of breast cancer, stages I, II or III
3. Completed primary treatment (chemotherapy, radiation and/or surgery) \geq 3 months and \leq 5 years prior to registration
4. May use concurrent adjuvant endocrine therapy or HER2-targeted therapy while on study
5. May use topical products (e.g., lidocaine) vaginally prior to penetrative vaginal sex
6. Ability to read and write English
7. Able to engage in sexual activity
8. Currently has a sexual partner
9. Responds “yes” to “Do you currently experience vaginal or vulvar dryness and/or pain with sexual activity?”
10. Responds “yes” to at least one of the following questions:
 - “Have you experienced negative changes in your body image since being diagnosed or treated for cancer?” or
 - “Have you experienced negative changes in your sexual desire since being diagnosed or treated for cancer?”

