Perform a hypnotic induction to focus on improving body-image; suggestions for visualizing a body as strong, healthy, and beautiful. Used during study weeks 5 and 6.

Goals:

- Increase relaxation

- Build on positive feelings about your body
- Improve feelings about your sexuality
- Improve sexual experience

Audio III: Hypnotic relaxation for sexual desire and energy

Perform a hypnotic induction to improve desire for intimacy and experience increased energy and sense of wellbeing. Used during study weeks 7 and 8.

Goals:

- Increase relaxation
- Build upon improved feelings about your body
- Build upon improved feelings about your sexuality
- Improve sexual desire and energy

VVA Control

The VVA control group will get the eight weeks of vaginal moisturizer exactly as described above for the intervention group. After completion of the eight weeks of the study, the women assigned to the VVA control will be offered the Hypnotic Relaxation Intervention to complete on their own off study.

Accrual: Our research team has successfully recruited cancer survivors into clinical trials with an average of 4-6 per month. Weekly and monthly accrual goals will be set and achieved through a multipronged recruitment approach.

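### The text describes no pre-treatment record of local vulvovaginal symptoms and no new-or-worsened rule, so events under the moisturizer will be hard to separate from symptoms present at entry

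*Combined protocol and SAP*

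**What the plan says.** On the harms, section 8.2 warns that with the moisturizer "participants may develop a vulvar rash or irritation; they may experience burning or itching; or they may experience a vaginal infection".

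On the women who enter, section 4.3.1 (item 9) requires a yes to "Do you currently experience vaginal or vulvar dryness and/or pain with sexual activity". Section 3.0 says that cancer treatments which remove estrogen "result in vulvovaginal dryness and discomfort, bleeding after intercourse, and increased susceptibility to infections".

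On when adverse events are assessed, section 10.0 reads "Adverse events (AEs) are not anticipated; however, study staff will assess AEs during follow up phone calls". Section 4.2 plans a remote contact for both groups two weeks (+/- 3 days) after the moisturizer starts, at which staff will "answer any questions about use of the moisturizer and assess for any adverse events". Calls then follow every two weeks. For the earlier visit, section 4.2 says "The purpose of the baseline visit is to ensure that participants understand the study requirements, have their questions answered, be consented, complete baseline questionnaires", followed by randomization. It lists no adverse-event or local-symptom inventory.

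On the comparator, section 4.4 says "The VVA control group will get the eight weeks of vaginal moisturizer exactly as described above for the intervention group".

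On analysis, section 7.0 has adverse events described and section 10.0 has them documented with CTCAE version 5. Neither defines a treatment-emergent event. Table 2 (section 4.5) has an adverse-event row, but its visit marks cannot be read in the text available here.

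**The concern.** Some of the harms named for the moisturizer resemble what the participants already have. A woman who reports irritation or burning at the two-week contact may have had it before the first application. The usual ways of telling are a pre-treatment record of the same symptom, or a comparison group not given the product. The second is absent by design, because both arms use the moisturizer. The first is not described in the text.

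Acceptability is part of the primary aim, and withdrawal reasons are to be reported by category. If a woman stops because of burning, the team will want to know whether the burning was new. The pilot is also meant to inform a larger trial, and symptom status before the first application cannot be collected afterwards except by recall.

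There is also a smaller point of wording. Section 10.0 says that no adverse events are foreseen, while section 8.2 lists specific local reactions that may occur.

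**Working it through.** The plan gives no adverse-event rate, so there is no figure of its own to reproduce. The check is a reading of the schedule, some timing arithmetic, and an illustration with assumed rates.

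**1. Where assessment is placed.** Sections 4.2 and 10.0 together place it at the two-week visit and the follow-up calls. Section 8.3 fits this: it pays $20 per two-week period, a period that includes the call and the adverse-event assessment, up to $80. That makes 80 / 20 = 4 periods, and 4 x 2 = 8 weeks, which is the treatment period with no separate baseline payment. This supports the reading of the prose but does not settle what Table 2 marks.

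**2. Timing of the first described assessment.**
- Days after first use: 14 - 3 = 11 to 14 + 3 = 17.
- Longest gap after the baseline visit: 14 days allowed before the start + 17 = 31 days.
- Planned applications (section 4.4): 14 daily, then 6 x 7 / 2 = 21 on alternate days, 35 in all. By day 14, 14 / 35 = 40% have been used.

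**3. What baseline data exist.** The FSFI covers lubrication and pain (section 5.0) and is completed at baseline (section 7.1). The PROMIS items cover lubrication and vaginal, clitoral and labial discomfort (section 5.0), and section 7.1 plans change from baseline for every patient-reported measure. As described, neither instrument covers rash, itching, burning or infection, and neither is linked to adverse-event grading. The demographic form takes a brief medical history, but is not described as recording these symptoms.

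**4. How far the overlap goes.** Item 9 concerns dryness and painful sex, and section 3.0 adds discomfort and a raised susceptibility to infection. Irritation and burning are close to these. Rash and a current infection are more distinct.

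**5. Illustration.** Let N = 30 (15 per arm, section 7.2), b = the assumed proportion with such symptoms at entry, and t = the assumed incidence among the rest. Suppose that every entry symptom persists and is counted at week 2. Then

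- symptomatic women = N x b + N x (1 - b) x t
- new cases = N x (1 - b) x t

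Each cell gives new cases / symptomatic women (share new):

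| b | t = 5% | t = 10% | t = 20% |
|---|---|---|---|
| 0% | 1.5 / 1.5 (100%) | 3.0 / 3.0 (100%) | 6.0 / 6.0 (100%) |
| 10% | 1.35 / 4.35 (31%) | 2.7 / 5.7 (47%) | 5.4 / 8.4 (64%) |
| 30% | 1.05 / 10.05 (10%) | 2.1 / 11.1 (19%) | 4.2 / 13.2 (32%) |
| 50% | 0.75 / 15.75 (5%) | 1.5 / 16.5 (9%) | 3.0 / 18.0 (17%) |

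The share runs from 100% down to 5%, depending on two quantities that the documents do not give.

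**The case against.** The strongest objection is that the central fact cannot be fully verified. Table 2 has a baseline column and an adverse-event row, and its marks are lost. This stands: a baseline check may be scheduled there. Even so, no rule for using such a record appears in the text.

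A reader might infer that new and old events cannot be told apart at all. The documents do not support that. FSFI and PROMIS give a partial reference for pain and discomfort, rash and infection differ from dryness or painful sex, and staff could ask about onset at each contact, although the plan does not say that they will.

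A reader might also infer from the lower rows of the table that most recorded events would be pre-existing. That rests on assumed prevalences, on symptoms persisting, and on staff recording unchanged symptoms as events. Section 3.0 cites considerable improvement by week 4 with daily moisturizer, and nothing says that unchanged complaints will be recorded. With low prevalence at entry, the problem largely disappears.

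A third inference would be that the wording in section 10.0 changes how events are classified for the IRB. Reporting follows institutional guidelines that are not in the documents, so this cannot be shown. A possible event is also not the same as an expected one.

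Finally, no aim promises a tolerability rate. Even with perfect ascertainment, 3 events in 30 women would give an exact 95% interval of about 2% to 27%. That limits how much the pilot can say about frequency, but it does not remove the value of knowing whether each event was new.

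**Conclusion.** The point holds in a limited form. On the text as it stands, and subject to the unreadable row in Table 2, adverse events are assessed only from about two weeks after the moisturizer starts (day 11 to 17). No pre-treatment record of the local symptoms in section 8.2 is described, and no new-or-worsened rule is given. Because women enter with vulvovaginal symptoms and both arms use the product, only change within each woman can separate new from existing events. For irritation and burning in particular, that will be hard with the data described. The baseline questionnaires close part of the gap.

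The size is unknown. The table in the working shows how much it depends on unstated rates and is not an estimate. The feasibility criteria in section 7.1 are not affected. This is an inexpensive improvement in measurement, worth making because the missing information cannot be recovered later. The mismatch between sections 8.2 and 10.0 is a matter of wording to reconcile.

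**What to change.** - **Baseline visit (section 4.2):** before the first application, ask about each symptom listed in section 8.2 and record its CTCAE v5 grade. If Table 2 already marks a baseline check, state its content in the text.
- **Later contacts:** use the same short list at the two-week visit and on every call.
- **Analysis (section 7.0):** tabulate as treatment-emergent only events that are new or of higher grade than at baseline. State that this shows change and not causation, since there is no group without the moisturizer.
- **Section 10.0:** reconcile its statement on anticipated events with the risks listed in section 8.2.

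The cost is a few added questions at an existing virtual visit and on existing calls, plus a short amendment to the text. One limit remains: treatment may start up to two weeks after the baseline visit, so a symptom that arises in that gap would count as new.
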